4.3.2. Duration of Stable Disease or Better

Definition

Duration of stable disease or better is measured from the start of the treatment until the criteria for progression are met.

Analysis method

Duration of SD or better will be analyzed using descriptive summary statistics. Subjects whose progression criteria are not met at clinical cut-off will be censored at the last adequate disease assessment.

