3.4. Extent of Exposure

Extent of exposure for ibrutinib will be summarized for the safety population by disease type and study cohorts. Descriptive statistics (n, mean, standard deviation, median, and range) will be provided for total number of cycles, treatment duration (the interval between date of first dose and date of last dose), and ibrutinib dosing information including total dose received (the sum of administered doses), dose intensity (the ratio of total dose and treatment duration).

Dose reduction for ibrutinib is defined as administered planned lower dose level. There is a one applicable dose level reduction for CLL/SLL cohort: 280 mg/day (level 1 reduction). There are two applicable dose level reductions in FL, DLBCL or Richter syndrome disease cohorts: 420 mg/day (level 1 reduction) or 280 mg/day (level 2 reduction). Dose reduction information will be summarized for the number of subjects with any dose reduction (at least 1 reported dose reduction), as well as the frequency and reason of dose reduction. Number and percentage of subjects with cycle delays will also be presented.

Dose interruption for ibrutinib is defined as missing/skipped dose for ≥ 7 day. The consecutive days of dose interruption are considered as 1 dose interruption. The number and percentage of subjects with dose reduction and dose interruption will be summarized. In addition, subjects with dose modifications (i.e., reductions or interruptions) and reasons for dose modifications will be summarized.

Extent of exposure for nivolumab will be summarized for the safety population by disease type and study cohorts. Descriptive statistics (n, mean, standard deviation, median, and range) will be provided for total number of infusion, infusion duration (the interval between the start time of infusion and the end time of infusion), infusion rate interruption duration (the interval between the start time of infusion interruption and the end time of infusion interruption), and nivolumab dosing information including, total dose administered/received (the sum of actual dose administered), total number of infusions interrupted, total number of infusions skipped, total number of infusions discontinued and total number of infusion rate reductions, interval between 2 consecutive infusions of nivolumab which is defined as end date of prior cycle to first day of following cycle.

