4.3. Exploratory Secondary Endpoints

4.3.1. Duration of Response

Definition

Duration of response is defined as the interval between the date of initial documentation of a response [PR(+L) or better] and the date of first documented evidence of PD (or relapse for subjects who experience CR during the study) or death, whichever occurs first. Subjects who are progression-free and alive, or have unknown status will be censored at the last adequate disease assessment.

Analysis method

Duration of response will be analyzed for subjects with PR(+L) or better. The distribution of duration of response will be estimated using the Kaplan-Meier method. The primary analysis will be based on response data by investigator assessment.

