5.5. Clinical Laboratory Tests

Laboratory data for hematology and serum chemistry tests, up to the later of the End of Treatment visit or up to + 30 days after last ibrutinib or up to 100 days after last dose of nivolumab whichever is last, will be reported in SI units. Applicable laboratory results will be graded according to NCI-CTCAE Version 4.03. Toxicity grading for creatinine increase is based on the NCI-CTCAE v4.03 criteria but limited only to the part based on the ULN, the other part that is based on change from baseline is not used for toxicity grading. Toxicity grading for all other lab parameters are based on the NCI-CTCAE v4.03 criteria as is.

The following laboratory tests will be analyzed:

- Hematology: hemoglobin, white blood cell count (WBC), absolute neutrophil count (ANC), absolute lymphocyte count (ALC), and platelet count
- Chemistry: sodium, potassium, magnesium, creatinine, creatinine clearance (CrCl), AST, ALT, alkaline phosphatase, LDH, total bilirubin, albumin, amylase and lipase.
- Beta2-microglobulin, serum immunoglobulin levels (IgG, IgM, IgA): only for FL and CLL/SLL disease cohorts.
- Coagulation panel: PT APTT and INR
- Thyroid function: T3 free T4 and TSH

Descriptive statistics (mean, standard deviation, median, and range) will be calculated for the raw data and for change from baseline at each time point of assessment, as well as for change from baseline to the last value. Worst toxicity grade will be summarized for all hematology and chemistry parameters except for LDH, which will be summarized by abnormal/normal using normal ranges. Change from baseline to the worst grade during the treatment will be provided as shift tables for selected parameters.

Lymphocytosis is defined as ALC increasing $\geq 50\%$ from baseline and achieving level $\geq 5 \times 10^9$ /L. Descriptive statistics will be provided for time to first lymphocytosis, i.e., time from first dose to date of first lymphocytosis. Similar to duration of response, Kaplan-Meier method will be used to estimate duration of first lymphocytosis as the time from first lymphocytosis to the earliest date of its resolution (i.e., when ALC decreased to the baseline level or lower or achieving level of $< 5 \times 10^9$ /L) or date of censoring (i.e., date of last non-missing ALC).

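### SAP 4.3.2 censors duration of stable disease but names only descriptive summary statistics, which understate it where follow-up is short relative to time to progression

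*SAP*

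**What the plan says.** SAP 4.3.2 defines duration of stable disease or better as "measured from the start of the treatment until the criteria for progression are met". The censoring rule is: "Subjects whose progression criteria are not met at clinical cut-off will be censored at the last adequate disease assessment". The method is: "Duration of SD or better will be analyzed using descriptive summary statistics". Nothing is said about how a censored time enters that summary.

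Elsewhere the SAP shows what it means by the term. In 3.4: "Descriptive statistics (n, mean, standard deviation, median, and range) will be provided for total number of cycles". In 5.5: "Descriptive statistics (mean, standard deviation, median, and range) will be calculated for the raw data".

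Other censored durations get a different method:
- Duration of response (4.3.1): "The distribution of duration of response will be estimated using the Kaplan-Meier method".
- PFS and OS (4.3.3): Kaplan-Meier.
- Lymphocytosis (5.5): "Kaplan-Meier method will be used to estimate duration of first lymphocytosis". The same paragraph gives time to first lymphocytosis by descriptive statistics, so the SAP treats the two as separate methods.

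No other section supplies a method. Protocol 12.4 and SAP 1.1 say only that the endpoint will be evaluated if the data are sufficient. SAP 2.4.1 gives only the subset (stable disease or better). SAP 4.3.4 also pairs censoring with a descriptive summary, for duration of symptom resolution.

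**The concern.** A mean, standard deviation, median or range has no place for a time known only to exceed some value. A programmer following 4.3.2 must either enter the censored times as if complete, drop them, or go beyond the text and use Kaplan-Meier. The first two understate the duration when many subjects are still progression-free at cutoff. In that setting a plain median largely reflects the cutoff date, not the disease.

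Duration of stable disease is a named secondary objective (Protocol 2.1). It would be reported beside a Kaplan-Meier PFS that starts from the same date, so two summaries of closely related quantities could disagree for no clinical reason.

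**Working it through.** The documents give no figure for this endpoint, so there is none to reproduce. The size can only be illustrated.

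**Inputs from the documents**
- Scans from Cycle 5, every 5 cycles for 15 months, then every 12 cycles; cycles last 14 days (Protocol Table 1).
- 1 month = 30.4375 days (SAP 2.7).
- Cutoff 6 months after the last subject's first dose, or earlier if that subject discontinues (SAP 1.2).
- Expected median time on therapy 2 months (DLBCL) to 15 months (CLL) (SAP 1.2); average about 6 months (Protocol 3.1).

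**Assumptions**
- Exponential time to progression with underlying median m = 2, 6 or 15 months, using time on therapy as a proxy.
- Uniform accrual over A = 6, 12, 18 or 24 months.
- Minimum follow-up F = 6, 12 or 18 months. F is varied because the cutoff is set by the last subject in the whole study, so a given cohort may have more than 6 months.

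**Step 1. Scan times.** Cycle 5 Day 1 is 4 × 14 = 56 days after the start; 56 / 30.4375 = 1.84 months. Adding 70 days each time gives 4.14, 6.44, 8.74, 11.04 and 13.34; then adding 168 days gives 18.86 and 24.38.

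**Step 2. Who is analysed.** Subjects progressing before the first scan are not stable disease or better. Their share is 1 − 2^(−1.84/m): 8% for m = 15, 19% for m = 6, 47% for m = 2.

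**Step 3. Median with complete follow-up.** An exponential time has no memory, so the median among those analysed is 1.84 + m, recorded at the next scan:
- m = 15: 16.84, recorded as 18.86.
- m = 6: 7.84, recorded as 8.74.
- m = 2: 3.84, recorded as 4.14.

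**Step 4. Effect of cutoff.** Each subject's follow-up lies between F and F + A. The recorded time is the first scan after progression if that falls before cutoff, otherwise the last scan before cutoff. With F = 6 and A = 6, nobody has more than 12 months, so no recorded time can exceed 11.04. A plain median therefore cannot reach 18.86, however slow the disease.

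**Step 5. Simulation, m = 15, all recorded times treated as complete, ranges over A**

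| Minimum follow-up | Censored | Plain median | Plain mean |
|---|---|---|---|
| 6 months | 55–76% | 6.4–11.0 | 7.3–12.3 |
| 12 months | 43–60% | 13.3 | between the rows above and below |
| 18 months | not tabulated | 18.9 | 14.0–17.6 |
| Complete | 0% | 18.9 | 25.6 |

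The median gap closes once nearly all censored times lie above the true median. The mean does not recover.

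**Step 6. Faster disease, F = 6.**
- m = 6: plain median 6.4 against 8.7 for A = 6 to 18, no gap at A = 24, and no gap at F = 12; mean 6.7–9.3 against 12.2.
- m = 2: plain median 4.1 against 4.1; mean at worst 5.4 against 6.1.

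**Step 7. One cohort of 35 treated subjects, m = 15, F = 6.** The Kaplan-Meier median is not reached in 87%, 78%, 37% and 15% of simulated cohorts for A = 6, 12, 18 and 24. The plain median still returns a number, averaging 7.0–11.2 months.

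**Step 8. Check without the scan grid or the exclusion in Step 2** (F = 6; A = 6, 12, 24). For m = 15, 46–66% are censored. The plain median is 7.7–10.5 against 15, and 4.0–6.8 if censored subjects are dropped. Kaplan-Meier gives 15, or not reached at A = 6. For m = 6 the plain median of all recorded times shows no gap (6.0 against 6.0), so the m = 6 median gap in Step 6 comes from the scan grid.

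**The case against.** **Descriptive need not exclude a Kaplan-Meier median.** A censoring rule has little purpose unless the analysis uses it, so Kaplan-Meier is a natural reading. That stands in part: a reader might infer that the SAP instructs censored times to be counted as complete, and it does not say that. But it names one method, defines that method elsewhere as uncensored summaries, and names Kaplan-Meier wherever else it wants it for the efficacy durations. Taken as written, the text does not lead to a valid summary.

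**The larger figures are pessimistic.** This stands. The row with 6 months' minimum follow-up assumes that the slow cohort finishes accrual last. Cohort B4 was added in March 2016, when B1 to B3 were already in the protocol, and SAP 2.1 pools Part A subjects into the disease types. CLL may therefore have longer follow-up; the documents do not say how much. Part of the 18.9 is also the scan grid, since the underlying value is 16.84.

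**Death.** A reader might infer that 4.3.2 wrongly censors deaths, because duration of response ends at progression "or relapse for subjects who experience CR during the study) or death, whichever occurs first", and PFS also counts death. The documents do not support calling that an error. Section 4.3.2 consistently describes a progression-only endpoint: the event is progression, and anyone without it is censored. It need not share its event with the other two. Any lengthening from censoring deaths depends on an assumed death share and on Kaplan-Meier already being in use, so it cannot be added to the effect above. What is missing is only an explicit mention of death.

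**Little depends on it.** Also true: Kaplan-Meier PFS carries much of the same information, with reasons for censoring, and tumour response is listed by visit.

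**Conclusion.** The point holds as a minor one. SAP 4.3.2 sets a censoring rule and names a method that cannot use it. Where time to progression is long relative to follow-up, the plain median can fall to between a third and three-fifths of its complete-follow-up value (6.4/18.9 = 0.34; 11.0/18.9 = 0.58) with 6 months' minimum follow-up. It is about 0.7 of that value with 12 months (13.3/18.9 = 0.70), and there is no large-sample gap with 18. The mean stays low throughout, at 7.3–17.6 against 25.6. In fast-progressing disease there is little or no effect.

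These sizes rest on exponential times, uniform accrual, time on therapy as a proxy for time to progression, and a minimum follow-up that the documents do not give by cohort. They show direction and order of size and are not forecasts.

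The endpoint sits under exploratory secondary endpoints, is conditional on sufficient data, and feeds no test or decision rule. ORR and the sample size are unaffected.

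**What to change.** In SAP 4.3.2, replace the descriptive summary with Kaplan-Meier estimation: median or not reached, 95% CI, number of events and number censored. Do the same in 4.3.4 for the censored duration of symptom resolution; time to resolution, summarised only in subjects who resolved, can stay as it is.

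As a clarification only, add a sentence to 4.3.2 saying whether death without progression is censored (the literal reading) or counted as an event as in duration of response and PFS.

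The cost is a few lines of SAP text. The programs for duration of response and PFS can be reused, and no data collection changes.

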4.3.3. Progression-free Survival and Overall Survival

Definition

PFS is defined as the interval between the date of first dose of study drug and the date of first documented evidence of PD (or relapse for subjects who experience CR during the study) or

death, whichever comes first. Subjects who are progression-free and alive, or have unknown status will be censored at the last adequate disease assessment.

OS is defined as the interval between the date of the first dose of study drug and the date of the subject's death from any cause. If the subject is alive at the time of the cut-off, it will be censored at the last known alive date (the last date among visit date, AE start and end dates, treatment date, disease assessment date, and survival follow up date, and if available, survival sweep date, etc.).

Analysis method

Similar analyses will be applied to OS and PFS as those used for duration of response. The distribution of PFS and OS will be estimated using the Kaplan-Meier method.

The primary analysis of PFS will be based on assessments by investigator. The reason of censoring will be summarized for OS and PFS. The median follow-up duration will be provided. Follow-up duration is defined as OS with reversed censoring, i.e., subject who died will be censored. The Kaplan-Meier method will be used to estimate the median follow-up.

4.3.4. Resolution of Lymphoma-related symptoms

Frequency and percentage of subjects with lymphoma-related symptoms will be summarized by cycle. All-treated population will be used.

For subjects who have reported symptoms at baseline and had at least one time point of assessment post baseline (before the start of subsequent therapy), the following summaries will be provided for the resolution of symptoms:

- Frequency and percentage of subjects who have no symptoms reported at least one post baseline time point (before the start of subsequent therapy)
 - Duration of resolution is defined as the interval between the initial time point of assessment when no symptoms was reported and the subsequent time point of assessment when symptoms re-occurred before symptoms re-occurred. Subjects who have no B-symptoms and alive will be censored at the last B-symptom assessment prior to subsequent therapy initiated. This will be summarized descriptively.
 - Time to resolution (applicable to subject with symptom at baseline) is defined as the duration from baseline to the first time point when no symptom was reported. It will be summarized descriptively for those subjects who experienced resolution.
 - As an exploratory analysis, subject's best response, will be summarized for those who experienced resolution.

5. SAFETY

Safety will be analyzed using the incidence, intensity, and type of adverse events, laboratory tests. All safety analyses will be based on the safety analysis set.

5.1. Adverse Events

The verbatim terms used in the CRF by investigators to identify adverse events will be coded using the current Medical Dictionary for Regulatory Activities (MedDRA). The severity of adverse events is assessed in NCI common toxicity criteria for adverse events (CTCAE) Version 4.03.

Treatment-emergent adverse events are 1) adverse events that occur after the first dose of study treatment, and up to + 30 days after last ibrutinib or up to 100 days after last dose of nivolumab whichever is last, or the start date of a subsequent systemic anticancer therapy, whichever is earlier (including both dates), 2) any adverse event that is considered study treatment - related (at least relationship to one drug of combination will be considered related) (i.e., possibly, probably, or very likely related to study drug) regardless of the start date of the event, 3) any adverse event that is present at baseline but worsens in severity and is subsequently considered drug-related by the investigator.

Treatment-emergent adverse events will be summarized by system organ class (SOC) and preferred term (PT), by severity, by relationship to study treatment, and by action taken. For each adverse event, the percentage of subjects who experience at least 1 occurrence of the given event will be summarized. Tables will be sorted by frequency in incidence (from the highest to lowest incidence). The same summary will be provided for drug-related adverse events, serious adverse events, and drug-related serious adverse events, immune-related events as well as adverse events leading to treatment discontinuation, and death.

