12.2. Safety Analyses

Adverse Events

The verbatim terms used in the eCRF by investigators to identify AEs will be coded using the most current version of the Medical Dictionary for Regulatory Activities (MedDRA). Toxicities will be graded for severity according to NCI-CTCAE, version 4. All reported AEs with onset during the Treatment Period (ie, treatment-emergent adverse events [TEAEs], and AEs that have worsened since baseline) will be included in the analysis.

Specifically, the following will be summarized:

- Incidence of DLT (Part A)
- All adverse events
- Grade 3 or higher adverse events
- Serious adverse events
- Adverse events leading to discontinuation of treatment

- Adverse events leading to death
- Adverse events of special interest

Summaries, listings, datasets, or subject narratives may be provided, as appropriate, for those subjects who die, who discontinue treatment due to an adverse event, or who experience a severe or a SAE.

Clinical Laboratory Tests

Laboratory data will be summarized by type of laboratory test. Reference ranges and markedly abnormal results (specified in the Statistical Analysis Plan) will be used in the summary of laboratory data. Descriptive statistics will be calculated for each laboratory analyte at baseline. Parameters with predefined toxicity grades will be summarized. Change from baseline to the worst grade experienced by the subject during the study will be provided as shift tables.

Vital Signs

Descriptive statistics of heart rate and blood pressure (systolic and diastolic) (supine) values and changes from baseline will be summarized. The percentage of subjects with clinically important changes from baseline will be summarized.

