13.1. Definitions

13.1.1. Adverse Event Definitions and Classifications

Adverse Event

An adverse event is any untoward medical occurrence in a clinical study subject administered a medicinal (investigational or non-investigational) product. An adverse event does not necessarily have a causal relationship with the treatment. An adverse event can therefore be any unfavorable and unintended sign (including an abnormal finding), symptom, or disease temporally associated with the use of a medicinal (investigational or non-investigational) product, whether or not related to that medicinal (investigational or non-investigational) product. (Definition per International Conference on Harmonisation [ICH])

This includes any occurrence that is new in onset or aggravated in severity or frequency from the baseline condition, or abnormal results of diagnostic procedures, including laboratory test abnormalities.

Note: The sponsor collects adverse events starting with the signing of the ICF (refer to Section 13.3.1, All Adverse Events, for time of last adverse event recording).

Serious Adverse Event

A serious adverse event based on ICH and EU Guidelines on Pharmacovigilance for Medicinal Products for Human Use is any untoward medical occurrence that at any dose:

- Results in death
- Is life-threatening
(The subject was at risk of death at the time of the event. It does not refer to an event that hypothetically might have caused death if it were more severe.)
- Requires inpatient hospitalization or prolongation of existing hospitalization
- Results in persistent or significant disability/incapacity
- Is a congenital anomaly/birth defect
- Development of a new malignancy that is not associated with the disease under study
- Is a suspected transmission of any infectious agent via a medicinal product
- Is Medically Important*

*Medical and scientific judgment should be exercised in deciding whether expedited reporting is also appropriate in other situations, such as important medical events that may not be immediately life threatening or result in death or hospitalization but may jeopardize the subject or may require intervention to prevent one of the other outcomes listed in the definition above. These should usually be considered serious.

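### SAP 5.1 item 3 makes a worsened baseline event treatment-emergent only if it is judged drug-related, which contradicts Protocol 12.2 and duplicates SAP item 2

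*SAP*

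**What the plan says.** Protocol 12.2 says which adverse events are analysed. Its parenthesis on events with onset in the Treatment Period reads "ie, treatment-emergent adverse events [TEAEs], and AEs that have worsened since baseline) will be included in the analysis". It sets no relatedness condition. Protocol 13.1.1 defines an adverse event without requiring a causal link and adds: "This includes any occurrence that is new in onset or aggravated in severity or frequency from the baseline condition". The same section starts collection at signature of the consent form.

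SAP 5.1 gives three alternative routes to treatment-emergent status:

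- **Item 1, timing:** "adverse events that occur after the first dose of study treatment". The window runs to 30 days after the last ibrutinib dose or 100 days after the last nivolumab dose, whichever is last, and is cut short by subsequent systemic anticancer therapy. Causality plays no part.
- **Item 2, relatedness:** "any adverse event that is considered study treatment - related", at the level of possible, probable or very likely, and "regardless of the start date of the event".
- **Item 3, worsening:** "any adverse event that is present at baseline but worsens in severity and is subsequently considered drug-related by the investigator".

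The definition decides what is tabulated: "Treatment-emergent adverse events will be summarized by system organ class (SOC) and preferred term (PT), by severity".

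**The concern.** A worsening item normally exists to catch events that were already there before treatment and became more severe on it, without asking whether the drug was to blame. Here the item asks exactly that. A pre-dose event that worsens on treatment is then tabulated or left out according to the investigator's attribution, although the Protocol includes it either way.

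Attribution is a weak filter in this trial. The study is open-label and has no control arm, and Protocol 13.1.2 assigns doubtful where another explanation, such as concomitant disease, is more likely. SAP item 2 does not count doubtful events. The overall treatment-emergent tables are the ones that should not depend on such judgements, since drug-related events have their own summary in SAP 5.1. That section plans the same summary for serious events and for events leading to discontinuation or death, so the definition may carry into those tables too.

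**Working it through.** The plan states no figure on this point, so the check is a logical comparison of the two rules.

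**Step 1: is item 3 redundant?** Let R be the set of events considered related, B those present at baseline, and W those that worsen.

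- Item 2 = R, with no restriction on start date.
- Item 3 = B ∩ W ∩ R.
- B ∩ W ∩ R is contained in R, so item 3 is a subset of item 2.
- Items 1, 2 and 3 together therefore admit the same events as items 1 and 2 alone.

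Item 3 adds no event. The only events it could usefully add are the unrelated ones in B ∩ W, and its own final clause removes them. That points to a drafting slip.

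**Step 2: apply both documents to an event that starts after consent but before first dose and worsens during treatment.**

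| Attribution and recording | Item 1 | Item 2 | Item 3 | SAP result | Protocol 12.2 |
|---|---|---|---|---|---|
| Related, kept on the original record | no | yes | yes | counted | included |
| Not related or doubtful, kept on the original record | no | no | no | not counted | included |
| Not related or doubtful, worsening entered as a new record with post-dose onset | yes | no | no | counted | included |

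The documents disagree only in the second row. Whether that row contains any events depends on how the case report form handles a change of grade. Neither document says.

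**Step 3: how many subjects?** For a cohort of 35 (Protocol 12.3) the expected number is 35 × w × u. Here w is the share of subjects with a pre-dose event that worsens and stays on its original record, and u is the share of those judged not related or doubtful. The documents give neither w nor u, so the number cannot be computed.

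**Step 4: does the whole SAP definition count fewer events than the Protocol?** This cannot be shown. The Protocol's Treatment Period ends at the End-of-Treatment Visit, planned within 30 days of the last dose (Protocol 3.1). SAP item 1 can run to 100 days after nivolumab, and item 2 has no time limit. The SAP can therefore add events that Protocol 12.2 leaves out, while losing those in the second row.

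**The case against.** The strongest reply is that item 1 already catches these events. Under Protocol 13.1.1 an aggravation from baseline is itself an adverse event, so one that happens after first dose is an event occurring after first dose, whatever its cause. Protocol 12.2 can be read the same way, since its parenthesis places worsened events under those with onset in the Treatment Period and does not strictly label them treatment-emergent. If sites open a new record at each worsening, nothing is lost.

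This reply limits the effect but does not remove the conflict. Neither document states that recording rule. If every worsening were a new post-dose record, item 3 would have no purpose. However Protocol 12.2 labels worsened events, it puts them in the analysis without a causality test.

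Three stronger readings are tempting, and the documents do not support them.

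- **A count of subjects.** Setting w at 10% to 30% and u at 50% gives 35 × 0.10 × 0.5 = 1.75 to 35 × 0.30 × 0.5 = 5.25, or about 2 to 5 per cohort. Those rates have no source in the documents, and the sum assumes that item 1 catches none of these events.
- **A loss concentrated in Grade 3 or higher cytopenias.** Eligibility does allow platelets down to 75 × 10⁹/L and haemoglobin down to 8 g/dL (Protocol 4.1). A low count that predates consent is a baseline condition and not an adverse event record, so its worsening after first dose would be a new event under item 1. The exposed events are those starting between consent and first dose, with screening up to 28 days. SAP 5.5 also reports worst grade for haematology and chemistry (LDH as normal or abnormal), with shift tables for selected parameters, and none of this depends on causality. Symptomatic events such as fatigue or diarrhoea have no such laboratory back-up.
- **A net under-count of treatment-emergent events.** The window comparison in the working shows why this does not follow.

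It is also fair to say that the bar for relatedness is low: possible is enough, and relation to either drug counts. That makes the excluded class smaller but does not empty it.

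**Conclusion.** The point holds as a contradiction between SAP 5.1 and Protocol 12.2, together with a redundant item in the SAP definition. One class of event is affected: onset between consent and first dose, worsening on treatment, judged not related or doubtful, and kept on its original record. Those events are in the Protocol's analysis and outside the SAP's treatment-emergent tables.

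The contradiction and the redundancy rest on the wording alone. The practical loss rests on one assumption, that at least some worsenings are not entered as new post-dose records. Its size is unknown. The efficacy analyses are not affected. The correction should be made because it is cheap and takes investigator attribution out of a table meant to be free of it.

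**What to change.** Reword item 3 along these lines: an event already present before first dose whose severity increases after first dose and inside the item 1 window, whatever its relationship to study treatment. Keep item 2 for related events.

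Deleting the causality clause alone is not enough. Item 3 would then have no end date, and an unrelated baseline event that worsened after subsequent anticancer therapy would become treatment-emergent, although item 1 stops at that point.

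Add one sentence on recording: whether a worsening opens a new adverse event record with its own onset date or changes the grade on the existing one, and how the program identifies it.

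The cost is a short text change, a minor programming change and slightly higher treatment-emergent counts. No information on causality is lost, because drug-related events remain summarised separately.
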